### 3.5.3.3 Active Control (Epoetin alfa) Subjects

Epoetin alfa subjects should maintain their Hb levels within the target range accepted by health authorities, specifically:

- Hb 10 to 11 g/dL in the United States (US)
- Hb 10 to 12 g/dL in countries outside the US

Hemodialysis subjects will be dosed IV TIW, with starting doses and dose adjustment rules according to the epoetin alfa USPI or SmPC. In subjects requiring ultra-low dose of EPO (eg,  $\leq 1000$  IU/per week), frequency of administration may be adjusted per local standard of care.

Home-hemodialysis and peritoneal dialysis subjects will be dosed according to the epoetin Package Insert or the SmPC or local standard of care.

For countries using prefilled syringes, the initial epoetin alfa dose and dose adjustments should be approximated to the closest weekly dose.

Note: Given the complexity in EPO dose adjustments and the need to take into account the various clinical parameters in EPO dose titration, one would not consider it a protocol deviation

when study subjects are dosed according to local standard of care whether or not it is concordant with package insert/SmPC

ESA administration in roxadustat subjects during hospitalization is not considered a protocol deviation if roxadustat is not allowed or available during that hospitalization.

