#### 3.6.3.2 Erythropoiesis Stimulating Agents (Roxadustat Arm Only):

The use of ESAs is not permitted during the Treatment Period, except if all of the following criteria are met:

- A subject's Hb level has not responded adequately despite two or more consecutive roxadustat dose increases or the roxadustat dose has reached the maximum dose limit
- Other causes for lack of response or declining Hb, such as iron deficiency, bleeding, acute inflammatory conditions, have been ruled out
- Reducing risk of alloimmunization in transplant eligible patients is a goal.

Roxadustat and ESA may not be co-administered. Treatment with an approved ESA may be initiated  $\geq$  3 days after the last roxadustat dose.

If the situation permits, the Investigator should inform the Medical Monitor prior to initiation of ESA therapy.

Subjects may receive **one course** of ESA rescue during the Treatment Period.

Erythropoiesis-stimulating agent rescue should stop after 4 weeks or once Hb exceeds 9 g/dL, whichever occurs first. If a subject requires more than 4 weeks of ESA rescue therapy due to inadequate Hb response, the Medical Monitor should be contacted.

Treatment with roxadustat may resume after the following intervals:

- Two days after stopping epoetin alfa
- One week after stopping darbepoetin alfa
- Two weeks after stopping methoxy polyethylene glycol-epoetin beta (Mircera®)

If more than one course of ESA rescue is required during the Treatment Period, the subject must be discontinued permanently from the study, and is considered a Treatment Failure.

Inadvertent ESA administration including ESA administration by hospital staff in Roxadustat subjects should not be counted as rescue unless above criteria are met; these subjects may be allowed to continue on study, if considered safe by the Investigator and Medical Monitor.

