#### 6.1.2.5 End of Treatment ( $\pm$ 7 days)

- Laboratory tests:
  - Complete blood count with WBC differential
  - Serum chemistry
  - Lipid panel (fasting whenever possible)
  - Serum iron, ferritin, TIBC, TSAT
  - CHr
  - HbA1c
  - Reticulocyte count
  - Special laboratory analytes
  - Archival serum/plasma samples (optional donation, separate consent form)
- Complete physical exam.

- Serum hCG test for women of childbearing potential (for definition, see [Section 3.6.6](#))
- Blood pressure, HR, temperature, respiration rate
- HRQoL questionnaires (SF-36, FACT-An, and EQ-5D-5L)
- 12-lead electrocardiogram
- Adverse event recording
- Concomitant medication recording
- Procedures and nondrug therapy recording

Erythropoiesis-stimulating agents may be started  $\geq$  3 days after the last dose of roxadustat.

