##### **8.4.4.1 Adverse Events**

Adverse events will be coded using the Medical Dictionary for Regulatory Activities (MedDRA).

An AE (classified by preferred term) occurring during the Treatment Period will be considered a TEAE if it was not present prior to the first dose of study medication, or if it was present prior to the first dose of study medication but increased in severity during the Treatment Period. An AE that occurs more than 28 days after the EOT/ET visit date will not be counted as a TEAE.

The number and percentage of subjects reporting TEAEs in each treatment group will be tabulated by system organ class and preferred term; by system organ class, preferred term, and severity; and by system organ class, preferred term, and relationship. If more than one event occurs with the same preferred term for the same subject, the subject will be counted only once for that preferred term using the most severe and most related occurrence for the summarization by severity and by relationship to the study medication.

The overall distribution of TEAEs by severity and relationship to study medication will be summarized by treatment group.

The proportion of subjects with TESAEs, fatal SAEs (ie, events that caused death), and AEs leading to discontinuation of study medication will be summarized by SOC, preferred term and treatment group.

Treatment emergent adverse events of interest will also be reported in terms of incidence rate per PEY.

Listings will be presented of subjects with SAEs, subjects with AEs leading to discontinuation, and subjects who died.

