12.1.1 Proportion of Subjects with TEAE

An AE (classified by preferred term) started during the treatment period will be considered a treatment-emergent adverse event (TEAE) if it was not present prior to the first dose of study medication, or it was present prior to the first dose of study medication but increased in severity during the treatment period up to 7 days after last dose of study drug or until the administration of another anemia drug (other than the randomized treatment). An AE that occurs more than 7 days after the last dose of study medication or after the administration of another anemia drug (other than the randomized treatment) will not be counted as a TEAE.

The number and percentage of subjects reporting TEAEs in each treatment group will be tabulated separately by system organ class and preferred term; by system organ class, preferred term, and severity; and by system organ class, preferred term, and relationship to study medication. If more than one event occurs with the same preferred term for the same patient, the patient will be counted only once for that preferred term using the most severe and most related occurrence for the summarization by severity and by relationship to the study medication.

The distribution of TEAEs by severity and relationship to study medication will be summarized by treatment group.

The incidence of common ($\geq 5\%$ of subjects in any treatment group) TEAEs, treatment-emergent serious AEs (TESAE), and AEs leading to discontinuation of study medication will be summarized by preferred term and treatment group, sorted in decreasing overall (across treatments) frequency. In addition, the incidence of death and fatal SAEs (i.e., events that caused death) and incidence rate per PEY will be summarized separately by treatment group and preferred term.

Listings will be presented of subjects with serious adverse events (SAEs), subjects with adverse events leading to discontinuation, and subjects who died.

Temporal profile of TEAEs of special interest may also be plotted by treatment group showing the subjects in the y-axis and time to these TEAEs in the x-axis (Appendix 8).

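### SAP 12.1.1 drops the protocol's rate per PEY for TEAEs of interest, and its anemia-drug cut-off, as worded, would discard on-drug AEs mainly in the roxadustat arm

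*SAP*

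**What the plan says.** **Rate.** Protocol 8.4.4.1 states: "Treatment emergent adverse events of interest will also be reported in terms of incidence rate per PEY". In SAP 12.1.1 a rate per PEY appears only for death: "the incidence of death and fatal SAEs (i.e., events that caused death) and incidence rate per PEY will be summarized separately by treatment group". TEAEs of special interest get an optional temporal plot. SAP 11.3.7 gives time to event and proportion for vascular access thrombosis. The remaining PEY measures in the SAP concern hospitalization, missed dialysis and Hb exposure.

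**Counting window.** The protocol's outer limit is: "An AE that occurs more than 28 days after the EOT/ET visit date will not be counted as a TEAE". SAP 12.1.1 shortens this to 7 days after last dose and adds that an AE "or after the administration of another anemia drug (other than the randomized treatment) will not be counted as a TEAE". The protocol's definition has no such clause.

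**ESA in the roxadustat arm.** Under Protocol 3.6.3.2, "Treatment with roxadustat may resume after the following intervals" following an ESA rescue course. Inadvertent or hospital-staff ESA "should not be counted as rescue unless above criteria are met; these subjects may be allowed to continue on study". Protocol 3.5.3.3 adds: "ESA administration in roxadustat subjects during hospitalization is not considered a protocol deviation if roxadustat is not allowed or available during that hospitalization". After treatment ends, Protocol 6.1.2.5 allows an ESA no sooner than "3 days after the last dose of roxadustat".

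**Exposure.** SAP 9.1 defines PEY from first dose to last dose, with no stop at an ESA.

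**The concern.** There are two gaps. First, an analysis that the protocol promises is not in the SAP text, and the change is not flagged, although Protocol 8.4.5 requires significant changes to be highlighted.

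Second, the sentence excluding AEs after another anemia drug stands as a condition of its own, separate from the 7-day limit, and has no restart. For a roxadustat subject an ESA is another anemia drug. For a control subject the randomized epoetin alfa is not. ESA rescue exists only in the roxadustat arm, and the protocol expects some of those subjects to return to roxadustat. Applied as written, the rule would discard their later on-drug AEs and lower the roxadustat TEAE percentages in an open-label comparison. Two programmers could reasonably code the sentence differently and obtain different safety tables.

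**Working it through.** **No figure to reproduce.** The documents quantify neither the anemia-drug clause nor ESA use by arm. The text comparison above carries the point, and the arithmetic below only shows scale.

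**Assumed inputs, none from the documents:** dosing time T = 2 years in both arms; true first-event rate h = 0.05, 0.10 or 0.20 per year, equal in both arms; share p of roxadustat windows closed by an ESA = 5%, 10% or 20%. Control windows are taken not to close.

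**One subject.** Day 1 first dose, ESA on Day 183, roxadustat resumed, last dose Day 730. PEY = 730/365.25 = 2.00 years. Time in which a TEAE can be counted = 182/365.25 = 0.50 years, a quarter of the exposure.

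**(a) Literal reading, windows close at a uniformly random time.**
- Control risk = 1 − exp(−hT).
- Roxadustat counted risk = (1 − p)[1 − exp(−hT)] + p[1 − (1 − exp(−hT))/(hT)].
- At h = 0.10 the control risk is 18.13%. The roxadustat risk is 17.69% (p = 5%, ratio 0.976), 17.25% (p = 10%, ratio 0.952) or 16.37% (p = 20%, ratio 0.903).
- Over all three values of h the ratios are 0.975–0.977, 0.951–0.953 and 0.902–0.907, that is 0.2–0.8, 0.5–1.5 and 0.9–3.1 percentage points lower.
- Dividing the same counts by first-to-last-dose PEY (T in both arms) leaves these ratios unchanged. Dividing by time at risk gives 1.00.

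**(b) Literal reading, informative closure.** In the same share p of both arms the event rate doubles after a random time u; only roxadustat windows close at u.
- Control risk in that share = 1 − exp(−hT)(1 − exp(−hT))/(hT). At h = 0.10 this is 1 − 0.8187 × 0.9063 = 25.8%.
- With p = 10%, control risk = 0.9 × 18.13% + 0.1 × 25.8% = 18.9%, against 17.25% for roxadustat: ratio 0.913.
- Over all h, the crude ratios for p = 5%, 10% and 20% are 0.95–0.96, 0.91–0.92 and 0.83–0.85. A rate over time at risk gives 0.98, 0.96 and 0.91–0.92, so a matched denominator alone removes about half of the shortfall.

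**(c) Hospital ESA given after the event that caused admission.** The percentage with a first TESAE is unchanged (1.00), because that event is counted before the window closes. For a later, different term, with L hospitalizations per year and ESA in a share q of them, counted risk = h/(h + qL) × [1 − exp(−(h + qL)T)]. With q = 10%, L = 0.3 closes 5.8% of windows and gives 0.971–0.973; L = 0.6 closes 11.3% and gives 0.943–0.946.

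**(d) Tail-only reading.** Suppose every roxadustat subject starts an ESA 3 days after last dose and loses 4 of the 7 tail days. The ratio is [1 − exp(−h(T + 3/365.25))]/[1 − exp(−h(T + 7/365.25))] = 0.995–0.996.

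**After the fix.** If all AEs between first and last dose count regardless of ESA, no window closes on treatment. The two arms then have the same formula in (a) and in (b), so the ratio is 1.00 in both, apart from the tail effect in (d).

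**The case against.** The strongest reply is that the clause was written for the post-treatment tail. It is paired with the 7-day limit, and an ESA can start 3 days after the last roxadustat dose, so a tail rule has an obvious purpose. In the first sentence of the definition, the phrase ending the window at another anemia drug can even be attached only to AEs that worsen in severity. A fully literal reading might also catch iron, which is encouraged in both arms and would close many windows in each; that is an unlikely intent. All of this stands as evidence that the text is ambiguous. It does not settle the matter, because the second sentence carries no limit to the tail.

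The reply also limits the size. Formal rescue is narrow: three criteria must all hold and only one course is allowed. A control subject given an ESA other than the randomized one would lose follow-up too, so the scenarios, which close roxadustat windows only, overstate the net asymmetry.

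Three stronger readings are tempting but not supported:
- A reader might infer that the SAP already produces a biased TEAE rate because PEY runs past the cut-off. It specifies no TEAE rate, and it does not say whether the death rate uses the TEAE window. The mismatch would arise only if the protocol's sentence were restored with SAP 9.1 PEY as denominator.
- A reader might infer that rates for TESAEs and for AEs leading to discontinuation were also dropped. The protocol specifies proportions for those.
- A reader might infer that the rate will not be produced at all. The table shells are a separate document and may contain it.

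Other planned outputs help only in part. The ESA rescue proportion (SAP 4.4, to Week 52) and ESA-weeks (SAP 11.3.4.2) describe use, not windows closed or time lost. Listings show individual events without adjusting the comparison. Adjudicated cardiovascular events go to the pooled SAP.

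**Conclusion.** Two wording gaps are established: the protocol's rate for TEAEs of interest is not carried into SAP 12.1.1, and the anemia-drug exclusion is not confined to the period after last dose. Followed as written, the exclusion would discard on-drug AEs mainly in the roxadustat arm and so favor roxadustat. Whether it would be followed that way, and how often, cannot be told from the documents. Under the assumed 5–20% closure the ratio of percentages would lie between about 0.90 and 0.98 with random closure, and between about 0.83 and 0.96 if closure marks subjects at higher risk. On the tail-only reading the effect is negligible. Because the size is unknown and a benign reading is plausible, this is a point to consider, not a defect shown to distort the safety comparison.

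**What to change.** 1. Amend SAP 12.1.1 so that the anemia-drug cut-off applies only after the last dose of study drug. All AEs from first to last dose should count in both arms, whatever ESA was given in between. If the sponsor wants the on-treatment cut-off, show it only as a sensitivity analysis, with the number of windows closed by another anemia drug in each arm.
2. Restore the protocol's rate for TEAEs of interest, beside the percentages, as first-event incidence per 100 patient-years. Time at risk should end at the first event or at the end of the same TEAE window, whichever is earlier, and not be the SAP 9.1 PEY. Name the TEAEs of interest, since neither document lists them.
3. Rates for TESAEs and for AEs leading to discontinuation are optional.

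The cost is a wording change and a few extra columns; dose, ESA and AE dates are already collected. The rate assumes a roughly constant hazard, which is why the percentages should stay alongside it.

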12.2 CLINICAL LABORATORY PARAMETERS

Descriptive statistics for laboratory values (in US conventional and SI units) and changes from baseline at each assessment time point will be presented by treatment group for the following laboratory parameters collected in the study including but are not limited to the following:

- Hematology: Hemoglobin, hematocrit, RBC count, MCV, MCH, MCHC, WBC count, WBC differential, platelet counts and Reticulocyte count;
- Chemistry: CPK, ALP, ALT, AST, total bilirubin, LDH, total protein, albumin, glucose, phosphate, uric acid, BUN, creatinine, sodium, and potassium; HbA1C;
- Serum iron, ferritin, TIBC, TSAT
- CHr
- Hepcidin
- CRP

Laboratory tests values are clinically significant (CS) if they meet either the low or high CS criteria. The number and percentage of subjects with post-baseline CS values will be tabulated by treatment group. The percentages are to be calculated relative to the number of subjects with available non-CS baseline values and at least one post-baseline assessment. The numerator is the total number of subjects with at least one post-baseline CS value. In addition, shift tables will be presented by treatment group and time point. The following 3 data listings will be presented by subject:

- A listing of lab values for all lab tests at all collected time points.
- A listing of subjects with post-baseline CS values will be provided including the baseline and post-baseline values.
- A listing of all AEs for subjects with CS laboratory values will also be provided.

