12 SAFETY ANALYSES

The safety analysis will be performed using the Safety Population. Safety parameters include adverse events, laboratory parameters, vital signs, ECG parameters, and physical examinations.

Safety interpretation will also be made based on analyses of composite endpoints derived from adjudicated events pooled across multiple studies in the roxadustat Phase 3 program per pooled statistical analysis plan (PSAP) on dialysis studies in the roxadustat program.

For each safety parameter, the last assessment made prior to the first dose of study medication will be used as the BL for all analyses of that safety parameter.

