12.3 VITAL SIGNS

Blood Pressures and Heart Rate baselines are defined as the mean of values obtained from the last 6 weeks of screening including Day 1 prior to the first dose. For subjects on hemodialysis, pre-dialysis vital signs will be used. For subjects on peritoneal dialysis, vital signs may be recorded at any time during the visit.

Descriptive statistics for vital signs (e.g., systolic and diastolic blood pressure, MAP, heart rate, and respiratory rate) and their changes from baseline at each visit and at the end of study will be presented by treatment group.

Vital sign values are potentially clinically significant (PCS) if they meet both the observed value criteria and the change from baseline criteria listed in Table 6 below. The number and percentage of subjects with post-baseline PCS values will be tabulated by treatment group. The percentages are to be calculated relative to the number of subjects with baseline and at least one post-baseline assessment. The numerator is the total number of subjects with at least one post-baseline PCS vital sign value. Shift tables may be presented. A supportive listing of subjects with post-baseline PCS values will be provided including the patient ID, study center, baseline, and post-baseline values. A listing of all AEs for subjects with PCS vital signs will also be provided.

Table 7. Criteria for Potentially Clinically Significant Vital Signs

Vital Sign Parameter	Flag	Criteria*	
		Observed Value	Change from Baseline
Systolic Blood Pressure (mmHg)	High	≥ 170	Increase of ≥ 20
	Low	≤ 90	Decrease of ≥ 20
Diastolic Blood Pressure (mmHg)	High	≥ 100	Increase of ≥ 15
	Low	≤ 50	Decrease of ≥ 15
Pulse Rate (bpm)	High	≥ 120	Increase of ≥ 20
	Low	≤ 50	Decrease of ≥ 20
Weight (kg)	High	-	Increase of ≥ 10%
	Low	-	Decrease of ≥ 10%

*A post-baseline pre-dialysis or post-dialysis value is considered as a PCS value if it meets both criteria for observed value and change from pre-dialysis or post-dialysis baseline.

Additional analyses include but are not limited to

- Subgroup analyses of patients without any change in BP meds during treatment period
- Proportion of subjects meeting NKF BP target: within sBP 120-140 mmHg/dBP 70-90 mmHg at baseline, during treatment, and 4 weeks post treatment

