12.4 ELECTROCARDIOGRAM (ECG)

Descriptive statistics for ECG parameters (e.g., Heart Rate, PR interval, QRS interval, QT interval, and QTc interval) at baseline and changes from baseline at each assessment time point will be presented by treatment group. QTc interval will be calculated using both Bazett ($QTcB = QT/(RR)^{1/2}$) and Fridericia ($QTcF = QT/(RR)^{1/3}$) corrections; and if RR is not available, it will be replaced with 60/HR in the correction formula.

A plot for each parameter of mean (+/- 95% CI) versus visit will be produced by treatment group (roxadustat vs. ESA).

ECG parameters values are potentially clinically significant (PCS) if they meet or exceed the upper limit values listed in Table 8 below. The number and percentage of subjects with post-baseline PCS values will be tabulated by treatment group. The percentages are to be calculated relative to the number of subjects with available non-PCS baseline and at least one post-baseline assessment. The numerator is the total number of subjects with at least one post-baseline PCS ECG value. Shift tables may be presented. A listing for all subjects with post-baseline PCS value will be provided including the patient ID, study center, baseline, and post-baseline PCS values.

In addition, a listing of all TEAEs for subjects with PCS ECG values and a listing of subjects with post-baseline significant ECG abnormalities as reported by the investigators will also be provided.

Table 8. Criteria for Potentially Clinically Significant ECG

ECG Parameter	Unit	Higher Limit
QRS interval	Msec	≥ 150
PR interval	Msec	≥ 250
QTc interval	Msec	> 500 ; Change from baseline > 60

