16.2.2 Repeated or Unscheduled Assessments of Safety Parameters

If a patient has repeated assessments prior to the start of study medication, then the results from the final assessment made prior to the start of study medication will be used as baseline. If end of study assessments are repeated or unscheduled, the last post-baseline assessment will be used as the end of study assessment for generating summary statistics. However, all post-baseline assessments will be used for PCS value determination and all assessments will be presented in the data listings.

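### SAP 12.2 and 12.4 take the CS/PCS numerator from all subjects but the denominator only from those not CS/PCS at baseline, so the percentage as written is not a true proportion

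*SAP*

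**What the plan says.** SAP 12.2 tabulates, by arm, subjects with post-baseline CS laboratory values. The percentage is taken "relative to the number of subjects with available non-CS baseline values and at least one post-baseline assessment". The next sentence reads "The numerator is the total number of subjects with at least one post-baseline CS value", with no condition on the baseline value.

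SAP 12.4 has the same structure for ECG. The denominator is "relative to the number of subjects with available non-PCS baseline and at least one post-baseline assessment", and the rule continues "The numerator is the total number of subjects with at least one post-baseline PCS ECG value".

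SAP 12.3, for vital signs, words its numerator in nearly the same way but takes the percentage "relative to the number of subjects with baseline and at least one post-baseline assessment". Subjects abnormal at baseline therefore stay in that denominator.

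Two general rules also bear on the point. Under SAP 12, "the last assessment made prior to the first dose of study medication will be used as the BL" for safety parameters. Under SAP 16.2.2, "all post-baseline assessments will be used for PCS value determination", so repeat and unscheduled results count. No other section of the protocol or SAP ties the laboratory or ECG numerator to the denominator set.

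**The concern.** The denominator in 12.2 and 12.4 is the one used for newly emergent abnormality: subjects already abnormal are not at risk of a first occurrence and are removed. The numerator is not restricted to match. A subject with, say, a PR interval above the limit on Day 1 and again at Week 24 adds one to the numerator and nothing to the denominator. A subject with no baseline value can do the same.

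Pre-existing abnormality would then be mixed into a figure that its denominator presents as new onset. A chance imbalance between arms in baseline abnormality would also show as a difference between arms on treatment. Randomization (Protocol 3.2) is stratified by region, screening Hb and cardiovascular/cerebrovascular/thromboembolic history, not by these laboratory or ECG values.

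**Working it through.** The documents report no figure for this percentage, so there is nothing to reproduce. The check is algebra on the two definitions, followed by assumed inputs.

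**Inputs**
- b = share of subjects CS/PCS at baseline. Not given; assumed 1% to 10%.
- r = chance that such a subject has a CS/PCS value after baseline. Not given; assumed 50% to 80%.
- q = chance that a subject not CS/PCS at baseline has one after baseline. Not given; assumed 2% and 5%.

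Subjects with a missing baseline are left out of the formula. They can only add to the numerator, so they push the figure further up.

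**Formulas**, per subject with a baseline and some follow-up
- As written: [b × r + (1 − b) × q] / (1 − b) = q + r × b/(1 − b).
- Numerator restricted to the denominator set: (1 − b) × q / (1 − b) = q.
- Excess: r × b/(1 − b). It is never negative and does not depend on sample size.

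**Results**

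| b | Excess, r = 50% | Excess, r = 80% | As written, q = 2% (r = 50% / 80%) | As written, q = 5% (r = 50% / 80%) |
|---|---|---|---|---|
| 1% | 0.5 points | 0.8 points | 2.5% / 2.8% | 5.5% / 5.8% |
| 2% | 1.0 | 1.6 | 3.0% / 3.6% | 6.0% / 6.6% |
| 5% | 2.6 | 4.2 | 4.6% / 6.2% | 7.6% / 9.2% |
| 10% | 5.6 | 8.9 | 7.6% / 10.9% | 10.6% / 13.9% |

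Example: b = 5%, r = 80% gives 0.80 × 0.05/0.95 = 4.2 points, so q = 2% is reported as 6.2%.

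**Imbalance between arms.** Let q = 5% and r = 80% in both arms, with b = 4% in one and 6% in the other. The rule gives 5% + 0.80 × 0.04/0.96 = 8.3% and 5% + 0.80 × 0.06/0.94 = 10.1%. The arms differ although nothing after baseline differs.

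**Not a true proportion.** With b = 50%, r = 90% and q = 20%, the result is 20% + 0.90 × 0.50/0.50 = 110%. These inputs are extreme and serve only to show that the ratio has no upper bound of 100%.

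**Which criteria are affected** (laboratory limits from SAP Appendix 3, ECG limits from SAP Table 8)
- Absolute limits, where b can be above zero: GGT, alkaline phosphatase, potassium, sodium, calcium, total protein, platelets, white cells, neutrophils, QRS, PR, and QTc above 500 msec if that is read as a criterion of its own.
- Relative to baseline, where b is zero by definition: creatinine and BUN (more than 1.5 times baseline) and QTc change above 60 msec.
- Limited by eligibility: inclusion criterion 10 (Protocol 4.1) admits ALT or AST up to 3 × ULN and total bilirubin up to 1.5 × ULN, the same levels at which Appendix 3 starts to flag. Few subjects should be CS at baseline on these tests.

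**The case against.** The strongest reply is that the SAP never says baseline-abnormal subjects are counted; it only omits to exclude them. The denominator sentence comes immediately before, so a programmer may well draw the numerator from that set, and the table shells, which SAP 1 places in a separate document, may say so. This stands as a limit on the claim: a reader might infer that the reported percentages are overstated, but the documents show only that they would be if the text is followed literally. It does not remove the defect. In 12.3 nearly the same numerator wording covers every subject with a post-baseline PCS value and is consistent there; in 12.2 and 12.4 only the denominator changes.

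A second reply is that new onset is not the only possible target. Using all subjects with a baseline in both parts, as in 12.3, is also coherent. With b = 5%, r = 80% and q = 2% that gives 0.05 × 0.80 + 0.95 × 0.02 = 5.9%, against 6.2% as written, a ratio of 1.05. Against the new-onset rate of 2.0% the ratio is 3.1. A reader might infer a several-fold inflation. That holds only if new onset is the target, and only under assumed rates, so no multiplier should be attached to the finding.

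Third, a reader might take these percentages to be the study's main laboratory and ECG safety summary. The documents do not support that. Protocol 8.4.4.2 and 8.4.4.4 call for descriptive statistics and changes from baseline, which the SAP also lists. Laboratory shift tables are planned, and listings show baseline beside post-baseline values. These let a careful reader see the problem, but they do not correct the percentage, and ECG shift tables are only optional.

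**Conclusion.** The mismatch is in the text of both SAP 12.2 and 12.4. Followed as written, the rule gives a ratio that is not a proportion of any set of subjects and that exceeds the new-onset rate by r × b/(1 − b).

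The direction is certain; the size is not, because the documents give no baseline abnormality or persistence rates. The range of about 0.5 to 9 percentage points rests entirely on the assumed b of 1% to 10% and r of 50% to 80%, and the excess is zero where nobody is abnormal or missing at baseline. It concerns the absolute-limit criteria only, with little effect on ALT, AST and bilirubin.

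The tables are descriptive. No primary, secondary or other hypothesis test uses them, and the adjudicated composite safety endpoints are covered by a separate pooled plan. The point is worth correcting because a stated rule yields a wrong figure and the correction is nearly free.

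**What to change.** In SAP 12.2, define the numerator as *the number of subjects in the denominator (non-CS baseline available and one or more assessments after baseline) who have any post-baseline CS value*. Make the same change in 12.4 with PCS in place of CS. The percentage then reports newly emergent abnormality, which the existing denominator already implies, and subjects with a missing baseline drop out of both parts.

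Subjects abnormal at baseline remain visible in the laboratory shift tables and in the laboratory and ECG listings. Because 12.4 leaves ECG shift tables optional, the listings may be the only place where they appear for ECG.

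The cost is two sentences in the SAP and one programming condition, with no new data.
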